6.1.1.1.2 External Beam Radiation Therapy

1. Patients will undergo a radiation planning CT and preferably, in those patient to get pelvic nodes treated, with intravenous contrast if clinically available. This will be done roughly 8 weeks after ADT. Patients will undergo a planning CT. Standard departmental protocol will be followed for simulation, including eligibility for intravenous contrast, patient immobilization, with a comfortably full bladder.

6.1.1.1.3 SBRT with CyberKnife

- 1. SBRT with the use of CyberKnife will occur roughly 6 weeks after initiation of EBRT. Standard departmental protocol will be followed for CK-SBRT preparation. Patients with seminal vesicle involvement are eligible and seminal vesicles will be covered with CK-SBRT only as clinical indicated.
- 2. The fusion of the PSMA PET/mpMRI scans with the planning CT will be carried out in the treatment planning software; the fiducials will be used for soft tissue registration. Initially, the T2w MRI sequence will be registered with the planning CT by mutual information registration via fiducials. If necessary, manual adjustments may also be applied during image registration. The PSMA-PET and rest of the MRI and PET-CT scans will share the registration between the T2w MRI scan and planning CT.
- 3. The GTV-MRI will be outlined as a joint effort between a radiologist and the treating radiation oncologist on the basis of the PI-RADs v2 criteria.³⁴⁻³⁵ Additionally, the GTV-PET will be contoured again jointly between the radiologist and radiation oncologist by 30% of the SUVmax value.²⁴ This will be done by taking into account all additional information (including tumor localization in the diagnostic biopsy and physical exam [palpation]). An additional volume (GTV-union) is created from both GTVs.
- 4. The GTVs (i.e. DILs), will be biopsied as a joint effort between the treating radiation oncologist and a urologist. Two cores will be taken per GTV.
- 5. Contouring of the prostate, rectum, and urethral will be performed per UNC standard practice and SBRT with CyberKnife will be performed per UNC standard practice.

- 6. Per UNC standard practice, if the CT or the MRI imaging shows suspicious pelvic nodes, these will be included in the radiation treatment field. If the PSMA imaging alone shows suspicious pelvic nodes, a biopsy of the suspicious node will be offered, and upon confirmation, these may be included in the radiation treatment field.
- 7. Because the PSMA-PET/CT may find distant disease that may otherwise not have been found, if the use of the PSMA-PET or MRI information suggests that the patient has M1 disease, the patient will be re-referred to the UNC multidisciplinary Urologic Oncology clinic for consultation to discuss 1) the implication of these findings, 2) what additional systemic agents should be used in their treatment regimen, if any, and 3) how these findings may impact the utility of this study. This would not exclude them from the study.

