2.4 Rationale

Radiation therapy is a standard curative option for patients with localized prostate cancer. At UNC, patients with unfavorable intermediate and high-risk prostate cancer are offered radiation usually given with a long course (18 months) of androgen deprivation therapy. The radiation can be given as moderately hypoefractionated radiotherapy alone, or with with a combination of conventionally fractionated external beam radiation therapy (EBRT) (25 daily treatments) and boost utilizing stereotactic body radiotherapy (SBRT) with CyberKnife (CK). Our standard practice is to include the pelvic nodes in our treatment field, although as previously discussed this topic is controversial. These are standard treatment options according to NCCN guidelines.³¹ With current standard radiation doses, 5-year recurrence-free survival is reported to be 83% (unfavorable risk disease). Additionally, when the radiation fields are designed, the primary tumor location within the prostate is not typically taken into account, rather, the entire prostate is treated uniformly.

The availability of the PET-MRI facility at UNC (Biomedical Research Imaging Center, BRIC) uniquely allows us to examine these clinically-relevant questions using an mpMRI/PSMA-PET scan. Patients participating on this trial will have, using the same injection, an mpMRI/PSMA-PET scan and a PSMA-PET/CT scan, both of which will be used to help with radiation design. The long-term goal of this line of research is to allow smarter radiation design in the future that more specifically targets the tumor(s), therefore maximizing the therapeutic window (by focusing treatment more where there is cancer and not treating where there is no cancer). There is significant long-term potential for this research as imaging continues to improve and PSMA-PET/mpMRI becomes more widely adapted. UNC's PET-MRI is one of only a few in the country, which positions UNC to be a leader in the development of this technology. This study will also help create new knowledge in terms of comparability of PET/MR and PET/CT, and how the information gained on PET/MR could potentially be transferred to PET/CT, the latter of which is more widely available.

Image-adapted prostate irradiation

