3.3 Exploratory Objectives

4.0 STUDY ENDPOINTS

4.1 Primary

The planning criteria that will be used are the current standard of care and standard practice at UNC and includes defined treatment volumes with a prescribed dose while respecting the dose constraints to all organs at risk. The primary endpoint is grade 3+ late genitourinary toxicity and gastrointestinal toxicity as classified and graded according to the National Cancer Institute's Common Terminology Criteria for Adverse Events (CTCAE), version 5.0 at 12 months after radiation therapy.

- 4.2 Secondary
- 4.2.1 Grade 3+ acute and late genitourinary and gastrointestinal toxicity will be defined according to CTCAE, version 5.0 during radiation therapy and at 1, 3, 6, 9, 12, 18, 24, 30, 36, 42, 48, 54 and 60 months post radiotherapy. Additionally, this will be reported as a cumulative incidence over the entire 5-year course of the study.
- 4.2.2 Biochemical control will be defined according to the Phoenix criteria³³ (PSA rise of 2 ng/mL over nadir) at 2 and 5 years after radiation therapy.
- 4.2.3 Patient reported quality of life will be measured using the Expanded Prostate Cancer Index Composite (EPIC-26) and the Urinary Obstruction/Irritation scale of the validated Prostate Cancer Symptom Indices (PCSI). Patient reported quality of life will be measured before the start of radiation therapy at 1, 3, 6, 9, 12, 18, 24, 30, 36, 42, 48, 54, and 60 months post radiotherapy.
- 4.2.4 The total number of subjects enrolled on the study will be compared to the total number of screened subjects.
- 4.2.5 The feasibility of meeting dose constraints will be defined as the proportion of subjects who meet the following dose constraint criteria:
 - SBRT-CK boost dose prescription: 6.5Gy x 3
 - PTV: V19.5Gy > 95%
 - PTVmax > 150%, CI < 1.8
 - CTV: V19.5Gy > 99%
 - \circ DIL: V24.0Gy > 99%

- SBRT-CK boost dose constraints:
 - o Rectum
 - V21.1Gy< 5 %
 - V18.9Gy< 20 %
 - V17.5Gy<10 %
 - V16.2Gy< 40 %
 - V10.2Gy< 60 %
 - V9.3Gy< 40 %
 - V19.5Gy<1cc
 - Max<21.2Gy
 - Bladder
 - V21.1Gy< 5 %
 - V19.5y < 5 cc
 - V9.3Gy<40 %
 - Max<21.2Gy
 - Prostatic Urethra
 - V19.5Gy > 95%
 - V22Gy < 0.03cc
 - Membranous Urethra
 - V18 Gy < 50%
 - Large bowel
 - V15Gy<1cc
 - Small bowel
 - V15Gy<1cc
 - Penile bulb
 - V15Gy< 3cc

4.2.6 Performance of PSMA-PET/MRI to PSMA PET/CT as defined as:

- Rate of identification and delineation of DIL (e.g. sensitivity and specificity)

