5.2.3 Inflammatory bowel disease

6.0 TREATMENT PLAN

6.1 Treatment Overview

6.1.1 Subsection for Radiation Delivery Details

6.1.1.1 Preparation process for radiotherapy

6.1.1.1.1 PET CT and MRI

- The subject will start ADT on the day of or after PSMA-PET/MRI. ADT can be administered at UNC or at Subject's local providers. Prior to radiation planning, the subject will have three MRI-compatible fiducials placed into the prostate by an urologist or radiation oncologist. These will be used for image registration purposes.
- 1-2 weeks after fiducial placement, the subject will undergo PSMA-PET/MRI (pelvis) scan at the BRIC. The subject will be injected with ~0.07 mCi/kg body weight ⁶⁸Ga-PSMA-11. Subject will undergo a PET/MR of the pelvis

CONFIDENTIAL UNIVERSITY OF NORTH CAROLINA July 24, 2024

with simultaneous acquisition of multi-parametric (mp)MR sequences and PET about 60 minutes after radiotracer injection (Siemens Biograph mMR). During the uptake period of 60 minutes, the subject should drink at least 500 mL of fluid (water or fluid of choice). The subject should void immediately prior to PET/MR acquisition. The MR sequences to be acquired are shown in Sequences of the mpMRI protocol). PET/MR acquisition takes A.6 about 30 minutes. Intravenous contrast will be administered for the mpMRI. All PET images will be reconstructed with corrections for attenuation, dead time, random events, and scatter, using iterative ordered-subsets expectation maximization. PET images in PET/MR will be acquired in list mode and reconstructed for several time points after scan start time and durations adjusted for radioisotope decay: e.g. 0-5 min, 5-10 min, 15-21 min and 21-28 min. No Lasix will be used for the PSMA-PET/MRI imaging acquisition. For the first five protocol subjects, if real-time reconstruction does not produce satisfactory images, the option to have the subject void (i.e. urinate) and reimage will be considered.

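### The PET-CT is told to reuse the registration computed for the T2w MRI, although it is a separate scan; this can bias the PET/MRI versus PET/CT lesion comparison if delineation is scored after that transform

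*Combined protocol and SAP*

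**What the plan says.** Section 6.1.1.1.3 item 2 describes a single computed registration: "the T2w MRI sequence will be registered with the planning CT by mutual information registration via fiducials". It then allows that "If necessary, manual adjustments may also be applied during image registration", and closes with the rule at issue: "The PSMA-PET and rest of the MRI and PET-CT scans will share the registration between the T2w MRI scan and planning CT".

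The two imaging examinations are described elsewhere. Section 6.1.1.1.1 has the PET/MR of the pelvis done "with simultaneous acquisition of multi-parametric (mp)MR sequences and PET about 60 minutes after radiotracer injection (Siemens Biograph mMR". Section 2.4 adds the second examination: "Patients participating on this trial will have, using the same injection, an mpMRI/PSMA-PET scan and a PSMA-PET/CT scan". It says that both scans serve radiation design.

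Section 4.2.6 compares PET/MRI with PET/CT. Its first component is "Rate of identification and delineation of DIL (e.g. sensitivity and specificity", judged against image-guided biopsy. The others are the rates of finding positive pelvic nodes and distant metastatic disease in the pelvis. Section 7.2.3 confirms that the research biopsy is there to estimate sensitivity and specificity of the two modalities. Section 10.3 gives no analysis for 4.2.6.

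**The concern.** A transform computed for one image set can be applied to another only if the two already share a coordinate frame. The PET and the other MR sequences meet that condition because they are acquired with the T2w series on one scanner. Nothing in the protocol establishes it for the PET/CT. Taken literally, the rule places PET/CT lesions in the planning frame with an offset equal to whatever difference in position exists between the two examinations.

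Delineation is a spatial property, and Section 2.4 names the comparability of PET/MR and PET/CT as something the study should teach. A positional error confined to one arm of that comparison could be read as poorer performance of PET/CT when it comes from data handling.

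There is also a question of consistency for treatment planning. Section 2.4 says both scans help with design. Section 6.1.1.1.3 item 3 and Section 6.1.1.2 define one PET volume without saying which PET it comes from, and PTV5 is GTV1 with a 0 mm expansion.

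**Working it through.** The plan states no registration error, lesion size or overlap, so there is no figure to reproduce. The check is textual, followed by an illustration on assumed values.

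**Step 1: which images share a frame with the T2w MRI?**

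- PET from the PET/MR: yes, by simultaneous acquisition (6.1.1.1.1).
- Other MR sequences: same PET/MR session (6.1.1.1.1).
- PET/CT: a separate scan from the same injection (2.4). Its scanner, positioning, timing and bladder preparation are not described. The instruction "The subject should void immediately prior to PET/MR acquisition" covers the PET/MR only, so it neither shows nor excludes a difference in bladder state.

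**Step 2: is the PET/CT aligned anywhere?** Item 2 contains one registration, with the T2w MRI as its source. No step registers the PET/CT to the T2w MRI or to the planning CT. The sentence on manual adjustment is general: it has no trigger, no tolerance and no recorded residual, and it does not mention the PET/CT.

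**Step 3: which results depend on the transform?**

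- Detection read on each scan's own images: no.
- Rates of positive nodes and of distant metastatic disease in the pelvis: no.
- Primary toxicity endpoint and sample size: no.
- DIL delineation, or matching of biopsy cores to lesions, done in the planning-CT or T2w frame: yes. The PET/MRI contour then carries only the error of the one computed registration. The PET/CT contour carries that error plus the uncorrected offset between scans.

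The order of items in 6.1.1.1.3 is relevant here: fusion is item 2, contouring item 3 and biopsy of the resulting GTVs item 4. If PET/CT contributes to those GTVs, the choice of biopsy site could also depend on the transform.

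**Step 4: how large could it be?** Assume one spherical lesion of radius r, drawn identically on both scans and then displaced by d. The overlap (Dice) of the two equal spheres is

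1 − 3d/(4r) + d³/(16r³).

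For a 10 mm diameter (r = 5 mm) and d = 3 mm: 1 − 9/20 + 27/2000 = 0.56. The same formula gives:

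| Assumed diameter | 2 mm shift | 3 mm | 5 mm | 8 mm |
|---|---|---|---|---|
| 10 mm | 0.70 | 0.56 | 0.31 | 0.06 |
| 15 mm | 0.80 | 0.70 | 0.52 | 0.28 |
| 20 mm | 0.85 | 0.78 | 0.63 | 0.43 |

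With no shift every entry would be 1.00. Neither the diameters nor the shifts come from the documents, and overlap is not a named endpoint. The table shows only that a shift of a few millimetres is not negligible against a lesion of this size.

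**Step 5: can fiducials support a separate registration?** Only if they are in place at imaging. Section 6.1.1.1.1 puts the PET/MRI 1 to 2 weeks after fiducial placement. Section 7.2.3 has the GTVs biopsied at fiducial placement, yet those GTVs are outlined from images that Section 6.1.1.1.1 schedules afterwards. Footnote 6 of the Section 8.1 table places fiducials during CyberKnife SBRT. These cannot all hold.

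**The case against.** The strongest reply is that the sentence is shorthand: the PET/CT is first aligned with the MRI set and then carried along, with manual adjustment available. A gross offset would be visible, and contouring is done jointly by a radiologist and a radiation oncologist using all available information. This is a possible reading, but the preliminary alignment is written nowhere, and Section 11.5 requires the study to be run as the protocol describes. Manual adjustment without a tolerance or a record does not make the comparison reproducible.

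The second reply concerns consequence, and much of it stands. A reader might infer that endpoint 4.2.6 is biased as planned. The documents do not support that: the reference is biopsy, no overlap or distance measure in planning-CT space is specified, and each scan could be read on its own images.

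A reader might also infer that the error goes directly into the boost volume through the 0 mm expansion. That requires the PET volume to be drawn from the PET/CT, which no section states. The primary objective speaks of PET/MRI as the basis for targets, and item 2 opens with fusion of the PET/mpMRI.

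Finally, the documents do not name the PET/CT scanner or describe its set-up, so no actual displacement can be asserted. The shared injection suggests that the two scans are close in time.

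**Conclusion.** The point holds in a conditional form. The protocol does more than leave the PET/CT registration unstated: it assigns to the PET/CT a transform computed for a different acquisition, with no step that would justify it. If delineation is scored, or cores are matched, after that transform, the misalignment works against PET/CT only and can bias this part of 4.2.6. The amount cannot be determined from the documents; the overlap figures rest entirely on assumed lesion sizes and shifts.

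This is a correction worth making to a secondary endpoint. It does not affect the toxicity test, the sample size, the nodal and metastasis rates or detection read on native images. Early closure does not remove it, because Section 10.3 applies the same analysis plan to whatever data are available.

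**What to change.** 1. In Section 6.1.1.1.3 item 2, limit the shared transform to images acquired in the PET/MR session.
2. For endpoint 4.2.6, register the CT component of the PET/CT separately to the T2w MRI or the planning CT. Record the residual error of both registrations.
3. In Section 4.2.6 or 10.3, state the frame in which DIL delineation is compared and biopsy cores are matched.
4. Reconcile Section 2.4, Section 6.1.1.1.3 items 2 and 3, and Section 6.1.1.2 on whether the PET/CT contributes to GTV-PET. How it should contribute is for the investigators to settle.
5. Reconcile Sections 6.1.1.1.1, 7.2.3 and 8.1 (footnotes 6 and 10) on when fiducials are placed, since a fiducial-based registration needs them present at both scans.

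The cost is one extra software registration per man, which can be run on images already acquired, and a few sentences of protocol text.

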6.1.1.2 Definition of Target Volumes

Gross Tumor Volume (GTV)

- GTV1 = fusion of the prostate GTV-PET and prostate GTV-MRI
- GTV2 = fusion of nodal GTV-PET and nodal GTV-MRI

Clinical Target Volume (CTV)

- CTV1 = Prostate + seminal vesicles
- CTV2 = Pelvic lymph nodes as defined by RTOG contouring guide³⁶
- CTV3 = Prostate + up to 1 cm of the involved seminal vesicles

Planning Target Volume (PTV)

- PTV1 = CTV1 + 7 mm (except posteriorly with a only 5mm expansion)
- PTV2 = CTV2 + 7 mm
- PTV3 = GTV2 + 5 mm
- PTV4 = CTV3 + 2 mm isotropically (but 5 mm on the side of disease) Rectum
- PTV5 = GTV1 + 0 mm Urethra/Bladder/Rectum

6.1.1.3 Radiation therapy planning

The irradiation technique will be a combination of EBRT and SBRT. The highest planning priority will be to satisfy the restrictions of the bowel, rectum and bladder (see below).

Dose on target volumes:

- PTV1: EBRT prescription dose of 45 Gy in 1.8 Gy/fraction for 25 fractions.
- PTV2: EBRT prescription dose 45 Gy in 1.8 Gy/fraction for 25 fractions
- PTV3: EBRT prescription with simultaneous integrated boost (i.e. dose painting) to 56.25 Gy in 2.25 Gy/fraction for 25 fractions

- PTV4: SBRT-CK prescription dose of 19.5Gy in 6.5Gy/fraction in 3 fractions.
- PTV5: SBRT-CK prescription dose of 24.0Gy in 8.0Gy/fraction in 3 fractions (satisfying first the dose constraints of the urethra, bladder and rectum). The maximum dose in PTV3 should be at least 3 mm away from rectum and bladder.

The planning priorities will be:

- 1. Compliance with standard planning criteria for external beam radiation and SBRT-CK in terms of prostate dose coverage and restrictions on normal tissue (urethra, bladder and rectum) (**Table 2**).
- 2. After #1 is met, an attempt will be made to place areas of increased dose heterogeneity, or hot spots, in PTV4+5.

Table 2 Dose Prescription and Normal Tissue Constraints used at UNC-Chapel Hill.

Structure	Goal (doses in Gy)			
External Beam				
PTV1, PTV2	At least 95% of volume at 45 Gy			
PTV3	At least 95% of volume at 56.26 Gy			
Bladder	At most 40Gy average dose			
Rectum	At most 10cm ³ volume at 40 Gy			
Femoral Heads	At most 0.1 cm ³ volume at 45 Gy			
Femoral Heads	At most 40 Gy at 10% volume			
Small bowel	At most 0.1cm ³ at 45 Gy			
CyberKnife therapy				
PTV4	V19.5 Gy > 95%			
PTV5	V24.0 Gy > 99% (satisfying first the dose constraints of the urethra, bladder and rectum)			
Rectum	V21.1Gy < 5 %			
	V18.9Gy < 20 %			

	July 24, 2024		
	V17.5Gy < 10 %		
	V16.2Gy < 40 %		
	V10.2Gy < 60 %		
	Max < 21.2 Gy		
	V20.1Gy < 1cc		
	V21.1Gy < 5 %		
Bladder	V19.5y < 5 cc		
	V9.3Gy < 40 %		
	V19.5 Gy < 5cc		
	Max < 21.2 Gy		
Large Bowel	V15Gy < 1cc		
	Max *** Gy (assuming a/b of large bowel to be 3 and *** cGy max dose from first course); BED would result in Max dose <60Gy in 1.8Gy/fx		
Small Bowel	V15Gy < 1cc		
	Max *** Gy (assuming a/b of large bowel to be 3 and *** cGy max dose from first course); BED would result in Max dose <54 Gy in 1.8Gy/fx		
Penile bulb	V15Gy< 3cc		
Testicles/	Max <1.1Gy		
Membranous Urethra	V18 Gy < 50%		
Prostatic Urethra	V19.5Gy > 95%		
	V22Gy < 0.03cc		

6.2 Toxicities and Dosing Delays/Dose Modifications

Any patient who receives treatment on this protocol will be evaluated for toxicity. Each patient will be assessed periodically for the development of any toxicity according to the Time and Events Table (Section 8.1). Patients will be evaluated during their external beam radiation therapy at least once/week while on treatment. Acute toxicity (<3 months) and/or late radiation associated toxicity (>3 months) will be assessed according to the NCI Common Toxicity Criteria for Adverse Events (CTCAE), version 5.0 (if appropriate). Treatment holds and delays and dose adjustments will be made according to the system showing the greatest degree of toxicity per these metrics. Neither dose modifications or treatment delays are anticipated and priority will be given to honoring normal tissue dose constraints (5.1.1.3).

For further information regarding PSMA please refer to the package insert: Galium Ga 68 PSMA-11 Injection

6.2.1 Radiation Dose Delays/Dose Modifications

For acute radiation toxicities, treatment breaks should be kept to a minimum. An effort will be made to complete the radiotherapy on schedule without significant treatment breaks, as prolongation of treatment is known to contribute to treatment failure. The need for radiotherapy breaks due to severe acute toxicity will be determined by the treating radiation oncologist. Patients on treatment are evaluated weekly by the radiation oncologist.

6.3 Supportive Care/Symptom Management

Patients who develop any adverse event while on study will receive standard of care treatment. Radiation and hormone therapy are already standard of care treatments for these patients. Standard of care treatments for known potential adverse events from these treatments are well established.

6.4 Definition of Dose Limiting Toxicity

A dose-limiting toxicity is defined as all Grade 3 or above acute toxicities attributed to the treatment under study. The accrual will be halted if the number of patients with dose-limiting toxicities equals to or exceeds a rate of 30%.

6.5 **Duration of Follow Up**

All patients will be followed for up to 5 years after radiation, or until death, whichever occurs first, after removal from study treatment for determination of study endpoints. Patients removed from study treatment for unacceptable adverse events (AEs) will be followed for resolution or stabilization of the AEs. All patients (including those withdrawn for AEs) should be followed after removal from study treatment as stipulated in the protocol.

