We denote p the probability that a patient experiences a late grade 2+ GU/GI toxicity. We want p to be small enough to claim the new imaging strategy (PSMA/PET-mpMRI) as feasible with no greater late toxicity. Specifically, the null and alternative hypotheses are:

$H_0: p \ge 0.30 \ vs \ H_1: p \le 0.15$

That is, we accept the claim that the new strategy is safe if the observed toxicity rate is not too high, and hope to reject the claim (H0) with sufficient power when the true toxicity rate is about 20%. With a sample size of 38, we reach 80% power to reject (if we observe ≤ 7 cases with late toxicity) the null hypothesis (H0) at alpha = 0.1. To account for 10% loss follow-up, we will enroll 42 patients to ensure 38 evaluable patients.

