10.2 Sample Size and Accrual

Accrual will take place at UNC. The design as proposed in the above section leads to 80% power at an alpha level of 10%. Taking into account that the dominant intraprostatic lesion (DIL, image-identified tumor in the prostate) can be safely defined in around 75% of the patients, and assuming a 10% patient drop-out (nonevaluable) rate, we will plan to enroll 42 patients in order to achieve the primary objective of this study. Based on a previous study conducted with a similar population, we anticipate averaged accrual of 2 patients per month, corresponding to 21 months to enroll 42 patients out of which we can accrue the 38 evaluable patients for this study.

Sequential boundaries will be used to suspend the trial if excessive grade 4 toxicity of any type, attributed to the treatment under study, is seen. If the study reaches a stopping boundary, it may be terminated by the PI, or submitted to the Data and Safety Monitoring Committee with a description of the failures to date and a rationale for why the study should be continued.

The accrual will be halted if the number of grade 4 toxicities is equal to or exceeds b_n out of n patients with full toxicity follow-up (see table below). This is a Pocock-type stopping boundary that assumes that a grade 4 toxicity rate of 0.05 is acceptable. If the true grade 4 toxicity rate is equal to 0.05, the probability of crossing the boundary is 0.20.

Number of Patients, n 1	2	3	4	5	6	7	8	9	10
Boundary, b _n 1	2	2	2	2	2	2	2	2	2
Number of Patients, n 11	l 12	13	14	15	16	17	18	19	20
Boundary, b _n 3	3	3	3	3	3	3	3	3	3
Number of Patients, n 21	1 22	23	24	25	26	27	28	29	30
Boundary, b _n 3	3	4	4	4	4	4	4	4	4
Number of Patients, n 31	1 32	33	34	35	36	37	38	39	40
Boundary, b _n 4	4	4	4	4	5	5	5		

In addition, grade 3+ toxicity (DLT) will also be monitored. The accrual will be halted if the number of grade 3+ DLTs is equal to or exceeds b_n out of n patients with full toxicity follow-up (see table below). This is a Pocock type stopping boundary that assumes that a DLT rate of 0.30 is acceptable. If the true DLT rate is equal to 0.30, the probability of crossing the boundary is 0.20.

Number of Patients, n 1	2	3	4	5	6	7	8	9	10
Boundary, bn -	-	3	4	4	4	5	5	6	6
Number of Patients, n 11	12	13	14	15	16	17	18	19	20
Boundary, b _n 7	7	7	8	8	9	9	9	10	10
Number of Patients, n 21	22	23	24	25	26	27	28	29	30
Boundary, bn 10	11	11	11	12	12	13	13	13	14
Number of Patients, n 31	32	33	34	35	36	37	38	39	40

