Boundary, b _n 14	14	15	15	15	15	16	17		

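### Sections 6.4 and 7.1.4 halt accrual at a 30% DLT rate, while Section 10.2 calls 30% acceptable and never halts below 41.7%

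*Combined protocol and SAP*

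**What the plan says.** Section 6.4 defines the event: "A dose-limiting toxicity is defined as all Grade 3 or above acute toxicities attributed to the treatment under study". It then gives a halting rule: "The accrual will be halted if the number of patients with dose-limiting toxicities equals to or exceeds a rate of 30" (per cent). Section 7.1.4 repeats both sentences. Neither section gives a minimum number of patients, a schedule of looks or a denominator, and neither refers to Section 10.2.

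Section 10.2 gives a second rule: "The accrual will be halted if the number of grade 3+ DLTs is equal to or exceeds" a tabulated count b_n among n patients with full toxicity follow-up. It describes the rule as follows: "This is a Pocock type stopping boundary that assumes that a DLT rate of 0.30 is acceptable". Its operating characteristic is: "If the true DLT rate is equal to 0.30, the probability of crossing the boundary is 0.20". The table runs from n = 3 to n = 38. Its last row, for n = 31 to 38, reads "14 14 15 15 15 15 16 17". The end point of 38 matches Section 10.1: "we will enroll 42 patients to ensure 38 evaluable patients".

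Section 10.2 introduces the DLT rule as an addition, but to the grade 4 boundary just above it. That wording does not link it to 6.4 or 7.1.4.

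**The concern.** Both rules are mandatory, both act on accrual and both concern grade 3+ DLTs. One treats 30% as the point at which to halt. The other treats 30% as tolerable and is built so that a trial running at that rate will usually continue. The same rate cannot do both jobs.

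The practical difficulty is plain. With 3 DLTs in 10 patients, or 6 in 20, the investigator and the Data and Safety Monitoring Committee have opposite instructions. Continuing breaches 6.4 and 7.1.4. Halting follows a rule whose error rate is nowhere stated and sets aside the only one for which it is. Section 11.5 requires the protocol to be followed exactly, so leaving the choice to whoever is monitoring is not a way out.

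**Working it through.** **Inputs.**
- 10.2 boundary b_n for n = 3 to 38: 3, 4, 4, 4, 5, 5, 6, 6 (n = 3–10); 7, 7, 7, 8, 8, 9, 9, 9, 10, 10 (11–20); 10, 11, 11, 11, 12, 12, 13, 13, 13, 14 (21–30); 14, 14, 15, 15, 15, 15, 16, 17 (31–38). There is no boundary at n = 1 or 2.
- Flat rule of 6.4 and 7.1.4: halt when DLT patients / n ≥ 0.30, so b_n = ceil(0.30 n).
- Last look at n = 38.

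**Method.** Patients are independent with DLT probability p. Let f_n(k) be the probability of k DLTs among n patients with no halt so far. Then f_n(k) = (1 − p) f_{n−1}(k) + p f_{n−1}(k − 1). At each look the mass at k ≥ b_n is removed and added to the halting probability.

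**Step 1: the plan's own figure.** With the 10.2 table, a look after every patient and p = 0.30, the halting probability is 0.2058. The stated 0.20 is reproduced. The n = 36 entry of 15 is slightly out of pattern; with 16 there, the result is 0.1999. This does not affect the point.

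**Step 2: the two thresholds side by side.**

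| n | Flat 30% rule | 10.2 table | Table as a proportion |
|---|---|---|---|
| 10 | 3 | 6 | 60% |
| 20 | 6 | 10 | 50% |
| 30 | 9 | 14 | 46.7% |
| 36 | 11 | 15 | 41.7% |
| 38 | 12 | 17 | 44.7% |

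The flat rule has the lower threshold at every tabulated n. The smallest b_n / n in the table is 15/36 = 41.7%, followed by 15/35 = 42.9%.

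**Step 3: halting probabilities by n = 38.**

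| Rule and looks | p = 0.10 | p = 0.20 | p = 0.30 |
|---|---|---|---|
| 10.2 table, after each patient | 0.2% | 3.3% | 20.6% |
| Flat 30%, each patient from n = 1 | 30.7% | 63.1% | 88.7% |
| Flat 30%, each patient from n = 5 | 14.2% | 49.6% | 84.0% |
| Flat 30%, each patient from n = 10 | 8.0% | 42.0% | 81.0% |
| Flat 30%, each patient from n = 20 | 1.3% | 25.1% | 72.1% |
| Flat 30%, looks at 10, 20, 30, 38 only | 7.4% | 38.8% | 78.1% |

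**Step 4: if both rules apply.** From Step 2, any count that reaches the table's boundary already meets the flat rule. When both are checked at the same looks, the table never decides anything. The trial's halting probability at p = 0.30 is then the flat rule's 72% to 89% under continuous checking, not 20%.

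**The case against.** Five points can be made on the other side.

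- **The sentence in 6.4 may be loose shorthand for the 10.2 table.** Both name DLTs, 30% and a halt to accrual, and 10.2 supplies the operating detail that 6.4 lacks. This is a possible account of how the text arose. But 6.4 and 7.1.4 speak of a number of patients reaching a rate, mention no boundary and do not point to 10.2. A reader of the safety sections would apply 30% as written.
- **Both rules can be obeyed by halting at the earlier trigger, and no patient is then less protected.** That is true, but it makes the printed table inoperative and leaves the trial with a halting probability that is stated nowhere.
- **The 0.20 is correct for its own table.** This stands. The 10.2 calculation is sound in itself; the fault lies in its relation to the other two sections.
- **The large halting probabilities at low true rates come from the first few patients.** This stands for p = 0.10: a single DLT among the first three patients meets the flat rule, and 1 − 0.9³ = 27.1 of the 30.7 percentage points arise there. It does not hold at p = 0.30, where starting as late as n = 20 still gives 72%.
- **The current version supports early closure, so an accrual rule has little left to govern.** This lowers the urgency. It does not resolve the conflict, and a report on whether the safety rule was met still depends on which rule was in force.

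**Conclusion.** The contradiction is real and sits in current text. At every tabulated n the two rules halt at different counts, and nothing ranks or links them. At a true DLT rate of 30%, which 10.2 calls acceptable, the choice of rule moves the chance of halting from 20.6% to between 72% and 89% under continuous checking. At a true rate of 20% it moves from 3.3% to between 25% and 63%.

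These figures assume independent patients, at most one counted DLT per patient, looks up to n = 38, and a check after each patient from the stated starting point. The ranges reflect the absence of a minimum n in 6.4 and 7.1.4. The conflict itself depends on none of these assumptions, since it follows from comparing the thresholds. Because it concerns the threshold for a mandatory safety stop, it needs correcting even though early closure reduces its practical weight.

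**What to change.** The sponsor, with the monitoring committee, should choose one accrual-halting rule for DLTs and state it once, in Section 10.2. The statement should give the denominator, the look schedule and any minimum n, and should print the probability of halting at several true DLT rates, for example 10%, 20% and 30%. The halting sentence in 6.4 and 7.1.4 should be replaced by a cross-reference to 10.2. If the table is kept, the n = 36 entry should be checked at the same time.

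Which rule is right is a clinical judgement about the tolerable rate of acute grade 3+ toxicity, and this review takes no position on it. Any report should name the rule that was in force while patients were being accrued. The cost is protocol wording and a short calculation, with no extra patients or visits.
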